5.3.3 Other Efficacy Endpoints

Percent change from baseline to week 52 in LDL-C will be analyzed using the ANCOVA method as described in section 5.3.1., using observed data (no imputation for missing data).

In addition, the same endpoint will be analyzed with patients in the FAS who did not receive additional lipid-lowering therapy by that time point (by week 24 and 52). Only observed case data will be used. Non-HDL-C, TC, ApoB and hsCRP at week 24 and 52 will be analyzed similarly using observed data.

The proportion of patients achieving LDL-C < 70 mg/dL at week 12, 24, and 52 will be summarized by treatment group and compared by Chi-sq test or fisher exact test. Only observed data will be used, i.e. the denominator will be number of patients who have LDL-C value at perspective time point.

TGs and HDL-C values at week 12, 24 and 52 will be summarized based on the FAS. For each parameter at each time point, the value of the parameter and the percent change from baseline in the parameter will be summarized by treatment group.

In cases where triglycerides (TGs) is >400 mg/dL or LDL-C is \leq 50 mg/dL, a measured LDL (LDL-M) will be used instead of LDL-C for the analysis of that time point. If both values are available, LDL-M will be used.

Baseline for each lipid is defined as the average of S1 (week -2) and predose Day 1/Week 0 values (the last two non-missing values on or prior to Day 1) with exception for apoB and hsCRP, for which predose Day 1 value will be used.

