#### **12.6.2. Other Efficacy Endpoints**

*Percent change or change in LDL-C, HDL-C, TG, TC, non-HDL-C, hs-CRP, and apoB values at other protocol-scheduled time points will be analyzed similarly using the ANCOVA model. The FAS will be used, with patients included in their randomized group, regardless of the treatment they actually received. No imputation for missing data will be performed.*

*For each parameter at each time point, the value of the parameter and the percent change from baseline in the parameter will be summarized by treatment group.*

*In addition, percent change from baseline to Week 24 and to Week 52 LDL-C will be analyzed with patients in the FAS who did not receive additional lipid-lowering therapy by that time point (by Week 24 for the Week 24 analysis; by Week 52 for the Week 52 analysis) included in the analyses. Only observed case data will be used (no imputation for missing data). Output from each time point will include the LSM and SE for each treatment group, as well as the placebo-correct LSM, 95% CI and p-value.*

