4.4 Sample Size Justification

A total of 1950 patients will be enrolled in this study with 1300 patients randomized to ETC 1002 and 650 patients randomized to placebo. Using an anticipated overall dropout rate of 7.5% at 6 months exposure and 10.0% at 12 months exposure in each treatment group, the expected number of patients exposed to treatment during the study is as follows:

	Patients \geq 6 Months	Patients \geq 12 Months
ETC-1002	1,202	1,170
Placebo	601	585

Absolute risk will be addressed by 1300 patients randomized to ETC-1002 and will provide at least 95% power to detect AEs that occur at rates similar to those seen in the placebo group for the AEs of interest in the recently completed long-term safety study entitled Efficacy and Safety of Alirocumab in Reducing Lipids and Cardiovascular Events [5]. In this study, adverse event rates ranged from 0.5% to 13.6%. Additional assumptions include a two-sided test with significance level at 0.05.

When AEs occur at a range of rates similar to those seen in the placebo group in the above referenced alirocumab study (0.5% to 13.6%), the sample size of 1300 patients randomized to ETC 1002 and 650 patients randomized to placebo will allow for detection of relative risks of 1.0 and of 2.0 (ETC-1002: placebo) with the following approximate 95% confidence limits:

% Placebo Patients Experiencing AE	% ETC-1002 Patients Experiencing AE	Relative Risk	Approximate 95% Confidence Interval
0.5%	0.5%	1.0	(0.3, 3.8)
0.5%	1.0%	2.0	(0.6, 6.7)
13.6%	13.6%	1.0	(0.8, 1.3)
13.6%	27.2%	2.0	(1.6, 2.5)

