5.3.2 Missing Data Imputation

Missing data in efficacy endpoints included in the step-down procedure will be imputed using a pattern mixture model (PMM) to specify different imputation strategies depending on whether the patient is still on study treatment. Patients with missing lipid data at Week 12 who are no longer taking study treatment (date of last dose of IMP is < week 12 visit date -7) can be assumed to no longer be benefitting from study medication, and their missing value(s) can be assumed to be similar to those from the placebo patients who have data. To account for uncertainty, missing values will be imputed using multiple imputation via a regression based model including stratification factor, baseline value and week 12 value using data from placebo patients only. In this imputation model, treatment group will not be included as a factor.

Patients with missing lipid data at Week 12 who are still taking study treatment (date of last dose of study medication is \geq date of week 12 visit -7) can be assumed to continue to benefit from study medication, and their missing value(s) can be assumed to be similar to those who remain on study treatment and have data and as a result, missing lipid values will be imputed based on the observed values in their randomized treatment group. To account for uncertainty, missing values will be imputed using multiple imputation via a regression based model including data from both treatment groups. In this imputation model, treatment group will be included as a factor.

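### Week 52 LDL-C is analysed on observed cases only, with no imputation-based analysis to show how far missing off-drug patients could inflate the one-year effect

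*SAP*

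**What the plan says.** SAP 5.3.3 provides that "Percent change from baseline to week 52 in LDL-C will be analyzed using the ANCOVA method", restricted to observed values. Protocol 12.6.2 agrees for time points outside the key set: "No imputation for missing data will be performed". Both documents add a second Week 52 analysis limited to FAS patients who received no additional lipid-lowering therapy, also on observed cases; the protocol asks for least-squares means, a confidence interval and a p-value from it.

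Imputation is reserved for the confirmatory sequence. SAP 5.3.2 says: "Missing data in efficacy endpoints included in the step-down procedure will be imputed using a pattern mixture model (PMM". That sequence (SAP 5.3) holds LDL-C at Weeks 12 and 24 and four other markers at Week 12. Under the rule, a patient with no lipid value who has stopped drug "can be assumed to no longer be benefitting from study medication" and is imputed from placebo data. A patient still on drug is imputed from a model that includes treatment group. The rule and the model are worded for Week 12 only.

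The observed-case and on-treatment sensitivity analyses in SAP 5.3.4 cover primary and key secondary endpoints. Week 52 LDL-C receives only a by-visit on-treatment summary. On attrition, SAP 4.4 works from "Using an anticipated overall dropout rate of 7.5% at 6 months exposure and 10.0% at 12 months exposure in each treatment group".

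**The concern.** The SAP uses observed-case analysis as a sensitivity method at Weeks 12 and 24 but makes it the only inferential method at Week 52, where planned dropout is highest. The values that go missing are unlikely to be a random sample. Patients who stop drug and decline clinic visits are followed by telephone, which yields no lipid sample, or leave follow-up altogether (Protocol 10.3.1, 10.2.8). These are the patients whom SAP 5.3.2 regards as no longer benefitting.

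At stake is an inferential one-year estimate in a 52-week trial. The reader never sees Week 52 under the assumption that the SAP itself prefers for the earlier time points. In addition, the leading estimates at Weeks 12, 24 and 52 follow different missing-data rules, so a profile over time built from them mixes drug effect with method.

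**Working it through.** **Inputs from the documents.** Randomization: "1300 patients randomized to ETC 1002 and 650 patients randomized to placebo". Dropout: 7.5% at 6 months and 10.0% at 12 months, in each arm (SAP 4.4). Off-drug patients with missing lipids: no effect relative to placebo (SAP 5.3.2).

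**Assumed, because the documents are silent.** D, the on-drug LDL-C effect against placebo: 10, 15 or 20 percentage points. r, the share of off-drug patients who have a Week 52 LDL-C: 0, 0.5 or 1.

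**Step 1: the plan's own figures.** 1300 × 0.925 = 1202.5 and 1300 × 0.90 = 1170; 650 × 0.925 = 601.25 and 650 × 0.90 = 585. These match the exposure table (1,202, 1,170, 601, 585). The plan gives no effect size, SD or power for LDL-C, so there is no efficacy figure to reproduce.

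**Step 2: size of the excess.** Let d be the share off drug by Week 52. Suppose that everyone on drug is observed and that off-drug patients have zero effect.

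- Observed-case effect = D(1 − d) / (1 − d + dr)
- Pattern-mixture effect = D(1 − d)
- Relative excess = m / (1 − m), where m = d(1 − r) is the share with missing LDL-C

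At d = 10%:

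| r | m | Relative excess | Excess in points, D = 10 / 15 / 20 |
|---|---|---|---|
| 0 | 10% | 0.10/0.90 = 11.1% | 1.0 / 1.5 / 2.0 |
| 0.5 | 5% | 0.05/0.95 = 5.3% | 0.5 / 0.7 / 0.9 |
| 1 | 0% | 0% | 0 / 0 / 0 |

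If 20% were off drug, an assumption above plan, the excess would be 0.20/0.80 = 25% at r = 0 and 0.10/0.90 = 11% at r = 0.5.

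**Step 3: comparison across visits.** Take a constant D of 15. The pattern-mixture estimate at Week 24 is 15 × 0.925 = 13.9. The observed-case estimate at Week 52 is 15.0 at r = 0, or 15 × 0.90/0.95 = 14.2 at r = 0.5. Averaged over all randomized patients, the Week 52 effect is 15 × 0.90 = 13.5. The headline figures would appear to rise while that average fell slightly.

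**Step 4: direction.** With 10% missing per arm and an observed effect of −15 points, the full effect is −15 + 0.10y − 0.10x. Here y and x are how much worse the missing active and missing placebo patients are than those observed in their arm.

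- y = 15, x = 0: −13.5
- y = 15, x = 15: −15.0
- y = 0, x = 15: −16.5

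Only the first case is an overstatement. Separately, adjunctive therapy is possible from Week 24 (Protocol 11.1.6.3.5). If 5% of placebo and 1% of active patients used it and it lowered LDL-C by 30 points (all assumed), the FAS difference would shrink by 0.04 × 30 = 1.2 points.

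**The case against.** A reader might infer that one-year efficacy is probably overstated, by about a tenth. The documents do not support that, for four reasons.

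- The 10% is dropout from exposure, not a rate of missing LDL-C. Patients who stop drug are asked to keep attending, with basic fasting lipids drawn (Protocol 10.3.1; SAP Appendix 1). The FAS keeps them in their randomized arm, and the Week 52 window is open-ended from Day 310 (SAP 5.1). That missingness peaks at Week 52 is therefore an inference, and 11% is a ceiling that needs no off-drug patient to return.
- Observed-case ANCOVA is unbiased if missingness depends only on arm, stratum and baseline. Step 4 shows that other patterns can bias it either way.
- Week 52 LDL-C is tertiary and outside the step-down sequence, the primary objective is safety, and neither document makes a formal claim of durability.
- SAP 5.3.4 already gives observed-case results for LDL-C at Weeks 12 and 24, so a like-for-like series is available.

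All four stand, and they limit both the size and the urgency of the point. They do not fill the gap: no planned analysis shows Week 52 under the SAP's own off-drug assumption.

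Two further objections bear on the remedy. The method in 5.3.2 cannot be carried over as written, because it refers to Week 12. And by Week 52 some observed placebo values may follow adjunctive therapy, so placebo-based imputation would carry that effect into the active arm. For the second reason, and because the stated tertiary objective concerns patients without adjunctive therapy, replacing the observed-case analysis would go too far.

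**Conclusion.** The point holds in limited form. Week 52 LDL-C rests on observed cases with no imputation-based check. If missing patients are off drug and resemble placebo, the effect is overstated by at most about 11% relative to the pattern-mixture estimate at the planned 10% dropout. That is 1 to 2 points for an assumed effect of 10 to 20 points, falling to about 5% and then zero as half or all of the off-drug patients return for lipids. The ceiling is tied to the planned 10% and would rise with greater attrition. The sign of the bias is not established. The issue is moderate: worth correcting because the estimate is inferential and the correction is cheap, but it touches no alpha-controlled claim.

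**What to change.** Add to SAP 5.3.3 or 5.3.4 a pre-specified pattern-mixture multiple-imputation analysis of Week 52 LDL-C in the FAS, reported beside the observed-case ANCOVA and not in place of it. The text should:

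- restate the on/off-treatment rule for Week 52, comparing the last IMP dose with the Week 52 target day, since a patient with no sample may have no visit date;
- put the Week 52 value, not the Week 12 value, in the imputation model;
- state how values recorded after adjunctive lipid therapy enter the placebo-based imputation;
- require the number of patients with missing Week 52 LDL-C, by arm and IMP status.

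The counts will show where in the 0 to 11% range the trial lies. The cost is SAP wording and one more imputation run, and the Week 52 estimate may come out slightly less favourable. If the data have already been unblinded, the analysis should be labelled post hoc.

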### 11.1.6.3.5. Monitoring and Management of Elevated LDL-C

An adjunctive therapy plan is in place for those patients whose LDL-C values meet the protocol-defined LDL-C threshold criteria. Post-randomization, LDL-C results will be masked to investigators in order to maintain the blind; however, the following thresholds have been set to notify investigators and provide an opportunity to adjust the patient's standard of care regimen.

- Beginning at Week 24 (Visit T5) visit and for the duration of the study, the central laboratory will notify the investigator when the patient's LDL-C value is  $>170 \text{ mg/dL}$  (4.4 mmol/L) and  $\geq 25\%$  from the patient's baseline value at Week 0, (Visit T1)
- Upon receiving notification from the central laboratory that the patient has met or exceeded the threshold criteria for LDL-C, the investigator will initiate the following adjunctive therapy plan:
  - Patients will be scheduled to return to the clinic within 1 week for a repeat fasting blood lipid sample to confirm that the LDL-C value meets the threshold criteria
  - After confirming that the LDL-C value meets or exceeds the threshold criteria, the investigator will adjust the patient's lipid-lowering treatment regimen per standard-of-care and local practice, with the exception of simvastatin *at doses  $\geq 40 \text{ mg/day}$*  and the fibrate, gemfibrozil. The patient's LDL-C will be re-evaluated at the next scheduled clinic visit as defined in the Schedule of Visits ([Appendix 1](#)).
  - The initiation of *any new or dose changes of any existing lipid-lowering treatment* will be documented on the eCRF as a concomitant medication with the associated start date
  - *Patients who have their lipid-lowering medications modified, including new medications or dosage changes to existing medications, should return to the clinic in 4 weeks after the modification to their lipid-lowering treatment for a routine safety laboratory assessment. Additional safety laboratory assessments may be conducted at the investigator's discretion. Patients receiving an average daily dose of simvastatin 40 mg based on lipid-lowering treatment modification, should adhere to the additional safety visits as described in [Sections 10.2.5](#) and [10.2.6](#).*
  - Adjunctive therapy medications will not be provided by the sponsor

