3.1 Objectives

The primary objective for this study is to evaluate the long-term safety and tolerability of ETC-1002 (bempedoic acid) versus placebo in high cardiovascular (CV) risk patients with hyperlipidemia (with underlying heterozygous familial hypercholesterolemia [HeFH] and/or atherosclerotic cardiovascular diseases [ASCVD]) who are not adequately controlled with their maximally tolerated lipid-modifying therapy.

The secondary objective is to assess the efficacy as the percent change from baseline to Week 12 in low-density lipoprotein cholesterol (LDL-C). This is the primary efficacy endpoint.

The tertiary objectives are:

- To assess percent change from baseline to Week 24 and to Week 52 in LDL-C in patients who do not receive adjunctive lipid lowering therapy.
- To assess high-density lipoprotein cholesterol (HDL-C), non-HDL-C, total cholesterol (TC), and triglycerides (TG) values at Week 12, 24 and 52.
- To assess apolipoprotein B (apoB) and high-sensitivity C reactive protein (hsCRP) values at Week 12, 24, and 52.

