5.2.8 Prior and Concomitant Medications

Prior medications are defined as medications that ended prior to the initiation of double-blind IMP. Concomitant medications are defined as medications that were ongoing at the time of double-blind IMP initiation or new medications that started post double-blind IMP initiation and within 30 days following the date of the last dose of IMP.

Medications, including prior statin medications, will be coded using WHO Drug (March, 2015, or later). The use of prior or concomitant medications will be summarized by treatment group, as well as overall, for the safety population according to Anatomical Therapeutic Chemical (ATC) class and coded medication name. Statin medications will be summarized separately. Prior and concomitant medications will be listed for each patient.

Number of patients receiving additional (post-randomization) adjunctive lipid-modifying therapy will be identified by medication class and will be summarized by the reasons for their additional treatment (hyperlipidemia or. hypertriglyceridemia) per concomitant medication CRF.

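### The Week 52 LDL-C analysis in patients without added lipid-lowering therapy drops patients because of their own on-study LDL-C, so it is not a randomised comparison and leans toward no effect

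*SAP*

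**What the plan says.** SAP 3.1 lists a tertiary objective: "To assess percent change from baseline to Week 24 and to Week 52 in LDL-C in patients who do not receive adjunctive lipid lowering therapy". SAP 5.3.3 implements it by restriction: "the same endpoint will be analyzed with patients in the FAS who did not receive additional lipid-lowering therapy by that time point", and adds "Only observed case data will be used". Protocol 12.6.2 plans the same analysis ("percent change from baseline to Week 24 and to Week 52 LDL-C will be analyzed with patients in the FAS", limited to those "who did not receive additional lipid-lowering therapy by that time point") and asks for least squares means, a 95% CI and a p-value.

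Protocol 11.1.6.3.5 governs when therapy is added for LDL-C: "Beginning at Week 24 (Visit T5) visit and for the duration of the study, the central laboratory will notify the investigator". The criterion has two parts, LDL-C above 170 mg/dL and at least 25% from the Week 0 value. A repeat fasting sample within one week must confirm it before the regimen is changed. Apart from these notices, LDL-C is masked to the investigator after randomisation. The only earlier lipid trigger is a confirmed triglyceride value above 1000 mg/dL, from Week 4 (protocol 11.1.6.3.6).

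SAP 5.3.3 does not define the additional-therapy flag or date its cut-off. SAP 5.2.8 counts added lipid-modifying therapy from the concomitant medication CRF. It treats a new medication as concomitant only if it starts after the first dose and "within 30 days following the date of the last dose of IMP". Patients who stop IMP are asked to continue visits, with basic fasting lipids, to Week 52 (protocol 10.3.1).

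**The concern.** The restriction looks harmless because it matches the objective's wording. But added therapy is a consequence of the outcome. A patient leaves the Week 52 set because LDL-C at Week 24 or Week 36 was high, and treatment affects that LDL-C. Removing the highest values mainly from placebo lowers the placebo mean and narrows the difference.

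The result would carry a CI and p-value without the protection of randomisation. It estimates neither the effect regardless of added therapy nor the effect had none been added. The second is the natural reading of the objective, and no other planned analysis provides it. The unrestricted Week 52 analysis includes LDL-C measured after therapy was added, which may be a PCSK9 inhibitor. The sensitivity models in SAP 5.3.4 cover only the primary and key secondary endpoints, so Week 52 LDL-C gets no more than an on-treatment by-visit summary.

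**Working it through.** **1. A figure to reproduce.** There is none. The sample-size section deals with exposure counts and adverse-event relative risks. Neither document gives an LDL-C mean, SD, effect size or power.

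**2. Timing.**
- Week 24: therapy prompted by the Week 24 sample needs a repeat first, so it starts after the value being analysed. The LDL-C rule therefore does not select patients for a Week 24 analysis whose cut-off is the sample date. If the cut-off were the end of the Week 24 analysis window, Day 211 (211 - 169 = 42 days past target), patients would be dropped because of the very value analysed. The SAP does not say which applies.
- Week 52: therapy prompted at Week 24 or Week 36 starts before the Week 52 sample, so the rule does select.

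**3. Why the arms lose different patients.** With baseline B and percent change P, the rule is B(1 + P/100) > 170 and P >= 25. The two parts coincide at B = 170/1.25 = 136 mg/dL. At B = 120 the rise must exceed 170/120 - 1 = 41.7%, and at B = 100 it must exceed 70%. Above 136 the 25% rise decides. If placebo averages 0 and active -16 (assumed), a placebo patient must lie 25 points above the arm mean and an active patient 25 + 16 = 41. At an SD of 25 that is 1.0 SD against 1.64 SD.

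**4. Size, by simulation (3,000,000 draws per scenario).** From the documents: 2:1 allocation, LDL-C at least 70 mg/dL at entry, and the trigger with its repeat, applied at Weeks 24 and 36. Assumed, with no source in the documents:
- log-normal baseline (mean/SD before the cut at 70: 100/30.5, 118/38, 148.5/50);
- true effect -16 points at every visit;
- SD of percent change 20 or 25;
- correlation 0.65 between visits, and 0.65 or 0.85 between a sample and its repeat;
- every triggered patient treated and nobody else, with the Week 0 and analysis baselines taken as equal.

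Triggered patients were dropped and Week 52 percent change was regressed on arm and baseline. Ranges run over the two repeat correlations.

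| Mean baseline (mg/dL) | SD of % change | Active dropped | Placebo dropped | Week 52 difference | Bias |
|---|---|---|---|---|---|
| 107 | 20 | 0.2-0.3% | 1.4-2.2% | -15.6 to -15.5 | +0.4 to +0.5 |
| 107 | 25 | 0.6-1.0% | 2.7-3.8% | -15.4 to -15.3 | +0.6 to +0.7 |
| 122 | 20 | 0.3-0.6% | 2.6-3.9% | -15.3 to -15.1 | +0.7 to +0.9 |
| 122 | 25 | 1.1-1.8% | 4.7-6.7% | -14.9 to -14.7 | +1.1 to +1.3 |
| 150 | 20 | 0.6-1.1% | 4.5-6.6% | -14.9 to -14.6 | +1.1 to +1.4 |
| 150 | 25 | 1.8-3.0% | 7.7-10.8% | -14.2 to -13.8 | +1.8 to +2.2 |

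With a true effect of 0 both arms lose the same share, and the bias is within 0.1 in every scenario. A separate run with a true effect of -15, correlation 0.5 and SD 20 to 30 gave +0.3 to +1.8.

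**5. Does imputation recover the effect?** The same data were used, with Week 52 values set to missing after the trigger and filled by regression on arm, baseline and pre-therapy values. Including the confirmatory samples (taken as available for everyone), the estimate was -15.9 to -16.1. Using scheduled visits only, in a run with nearly the same baselines, it was -15.7 to -15.9. The recovery is expected, because therapy in the simulation depends only on recorded values.

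**6. Medication window.** If the SAP 5.2.8 limit applied and the last dose were on Day 85, the window would close on Day 85 + 30 = 115. That leaves 365 - 115 = 250 days to Week 52 in which a new drug would go uncounted.

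**The case against.** The restricted analysis is tertiary, is introduced as an addition, and lies outside the step-down. Week 24 LDL-C on the full FAS with imputation is the second test, and an unrestricted Week 52 analysis is planned. The subset follows the objective as worded, and SAP 5.2.8 will report how many patients received added therapy. The bias is toward no effect, so this mechanism cannot manufacture efficacy. Imputing the removed values answers a hypothetical question, which may not be what the sponsor meant. All of this stands and limits the weight of the point. It does not turn the subset result into a randomised comparison.

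Two stronger readings are tempting and should not be made. A reader might infer that the Week 24 analysis is selected in the same way. The trigger begins with the Week 24 sample and needs a repeat, so that is true only if the cut-off means Day 211. A reader might also infer that therapy started more than 30 days after the last dose will be missed. SAP 5.3.3 never cites the SAP 5.2.8 definition, and the protocol requires new or changed lipid-lowering treatment to be recorded with its start date. What the documents support is that the flag is undefined. Any resulting error could go either way, depending on which arm has more such patients.

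**Conclusion.** The point holds for Week 52. The restricted LDL-C comparison is selected on a treatment-affected outcome and is biased toward no effect if the drug lowers LDL-C and investigators act on the notices. The bias is about 0.4 to 2.2 points on an assumed true -16, and zero with no effect. The size rests wholly on the assumptions listed and on the confirmatory repeat being applied; leaving the repeat out would overstate it. The direction depends much less on them. A reader might infer that the trial's efficacy conclusions are in doubt. The documents do not support that, since the step-down and the unrestricted FAS analyses at Weeks 24 and 52 do not use this subset. The change should be made because this is the only analysis planned for a stated objective, but it is not critical to the trial's main conclusions.

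**What to change.** - For the no-added-therapy objective, keep every FAS patient. Set LDL-C after the start of additional lipid-lowering therapy to missing and multiply impute it from arm, stratum, baseline and pre-therapy values, including the confirmatory repeat sample.
- Define the additional-therapy flag from all post-randomisation medication records up to the date of the LDL-C sample analysed, whatever the last IMP date. This settles both the Week 24 cut-off and the 30-day ambiguity.
- Keep the subset result as a descriptive table without a p-value, beside the unrestricted FAS result.

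The cost is SAP wording and programming; no new data are needed, and SAP 5.3.2 already uses multiple imputation. The downside is an assumption that the SAP should state: given the recorded earlier values, starting therapy carries no further information about later LDL-C. Therapy added at discretion, outside the LDL-C rule, may not satisfy it.

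### The exploratory LDL-C <70 mg/dL responder comparison is unadjusted and counts only patients with a value, so it loses some precision, is not an all-randomised estimate, and may overstate the difference slightly

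*SAP*

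**What the plan says.** SAP 5.3.3 has the proportion of patients with LDL-C below 70 mg/dL at Weeks 12, 24 and 52 "summarized by treatment group and compared by Chi-sq test or fisher exact test". On the denominator it says: "Only observed data will be used, i.e. the denominator will be number of patients who have LDL-C value at perspective time point". It names no covariate, stratification, effect estimate or confidence interval for this endpoint.

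Other parts of the SAP set a different standard for LDL-C:

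- SAP 5.2.1.2 and 5.3 assign all efficacy analyses to the FAS, defined as all randomised patients.
- SAP 5.3.1 analyses percent change in LDL-C with randomisation stratum and baseline value in the model.
- SAP 5.3.2 imputes missing values, but only for step-down endpoints. Its premise is that a patient without a lipid value who has stopped treatment "can be assumed to no longer be benefitting from study medication", and that "their missing value(s) can be assumed to be similar to those from the placebo patients who have data".
- The alternative analyses of primary and key secondary endpoints in SAP 5.3.4 do not extend to the responder endpoint.

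The SAP's summary of changes (item 14) calls the responder analysis exploratory, and SAP 5.3 leaves it out of the step-down list.

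**The concern.** Two features look weak.

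**No adjustment.** Whether a patient ends below a fixed 70 mg/dL depends on where that patient started. Baseline LDL-C and stratum are already collected and already used for the continuous endpoint, so omitting them gives up precision for nothing.

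**The denominator.** Patients without a value drop out of both numerator and denominator. If some of them, in the active arm, have stopped drug and behave like placebo patients, the observed active-arm rate is higher than the rate among all randomised patients. The difference then leans towards the drug. At Weeks 12 and 24, the responder percentages would also stand beside a main LDL-C result that rests on another missing-data assumption, with no sensitivity analysis to show whether that matters.

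At stake are the size and precision of a descriptive responder difference. No confirmatory claim depends on it.

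**Working it through.** **Inputs from the documents.** SAP 4.4: "1300 patients randomized to ETC 1002 and 650 patients randomized to placebo". SAP 4.4, dropout: "Using an anticipated overall dropout rate of 7.5% at 6 months exposure and 10.0% at 12 months exposure in each treatment group". No dropout figure is given for Week 12, and no response rate or power for the responder endpoint.

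**The plan's own figures.** Expected patients exposed = N x (1 - dropout).

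- 6 months: 1300 x 0.925 = 1202.5 and 650 x 0.925 = 601.25. The SAP gives 1,202 and 601.
- 12 months: 1300 x 0.90 = 1170 and 650 x 0.90 = 585, as the SAP gives.

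These reproduce. They are the only figures in the SAP that bear on missingness.

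**Denominator effect.** Let pA and pP be the response rates among measured patients, and m the share of the active arm that is both off drug and unmeasured.

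- Observed-case difference: pA - pP.
- All-randomised difference under the 5.3.2 premise: [(1-m)pA + m pP] - pP = (1-m)(pA - pP).
- Ratio of the two: 1/(1-m). Overstatement: m(pA - pP).

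This takes the unmeasured patients to have the average placebo response rate. Counting missing patients as non-responders gives the same result when missingness is equal in both arms. With assumed rates of 30% and 9% (not in the documents), the observed-case difference is 21.0 points:

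| m | 1/(1-m) | All-randomised difference | Overstatement |
|---|---|---|---|
| 2% | 1.02 | 21 x 0.98 = 20.6 | 0.4 |
| 5% | 1.05 | 21 x 0.95 = 20.0 | 1.0 |
| 7.5% | 1.08 | 21 x 0.925 = 19.4 | 1.6 |
| 10% | 1.11 | 21 x 0.90 = 18.9 | 2.1 |

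For other assumed rate pairs, the overstatement at m=10% is 0.10 x (20-5) = 1.5 points and 0.10 x (40-15) = 2.5 points.

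**Plausible size of m.** Protocol 10.3.1 and the note to SAP Appendix 1 keep basic fasting lipids in the follow-up of patients who stop IMP but still attend clinic. Those patients have a value and stay in the denominator. Only patients followed by telephone, or who leave the study, have none. So m is probably below 7.5% at Week 24 and below 10% at Week 52.

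**Precision.** Simulated trials of 1300 against 650 patients compared the treatment test statistic without and with baseline LDL-C in the model. The assumed inputs, none from the documents, were baseline LDL-C about 103 mg/dL (SD 30) truncated at 70, and SD of percent change 22.

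| Assumed effect | Mean z, unadjusted | Mean z, adjusted | Ratio | Repeat run |
|---|---|---|---|---|
| -16% | 7.77 | 8.24 | 1.06 | 7.72 to 8.17 (1.06) |
| -8% | 3.89 | 4.12 | 1.06 | 3.73 to 4.01 (1.08) |
| -4% | 1.85 | 1.99 | 1.08 | 1.78 to 1.95 (1.10) |

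Five further assumed scenarios gave ratios of 1.08 to 1.10. The equivalent gain in patients is the squared ratio: 1.06 x 1.06 = 1.12 and 1.10 x 1.10 = 1.21, so roughly 12-20%.

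The gain depends on the inputs. A wider set with baseline truncated at 65 and SD of change 18-25 gave ratios from 8.15/7.61 = 1.07 to 6.97/5.97 = 1.17. Because Protocol 7.1 requires a screening LDL-C of at least 70 mg/dL, the lower cut is further from the entry rule, and the conclusion uses 6-10%. Strata were not simulated.

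**The case against.** The case for leaving the plan alone has real weight.

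- **The endpoint is exploratory.** It carries no alpha. This stands, and it sets the severity.
- **An unadjusted test of randomised proportions is valid.** This also stands. The SAP itself uses an unadjusted Wilcoxon test for hsCRP, a step-down endpoint. The argument for adjustment is efficiency, not correctness.
- **Observed-case analysis is a declared convention.** Protocol 12.6.2 and SAP 5.3.3 apply it outside the step-down, and SAP 5.3.3 applies it to Week 52 percent change in LDL-C. So at Week 52 the responder analysis already matches the continuous one on missing data. The mismatch with the main analysis is confined to Weeks 12 and 24.

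A reader might infer that the plan drops patients who stop drug. It does not. It drops patients without a value, whether on or off drug. Nor does every missing value favour the drug: a patient who misses a visit while still on treatment adds no such bias, and the second rule in 5.3.2 treats that patient like others in the same arm who have data.

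A reader might also take the bias to be 10-15% of the difference. A value of m=10% uses the entire anticipated 12-month dropout, and 15% is above any dropout figure in the documents.

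What remains is that the FAS promise is not met for this endpoint, no planned analysis shows how much the unmeasured patients matter, and available covariates go unused.

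**Conclusion.** The point holds at low severity. The responder comparison omits baseline LDL-C and the strata, and it is not an all-randomised estimate. Adjusting for baseline LDL-C would raise the test statistic by about 6-10% (roughly 12-20% more patients), on assumed baseline and variability figures.

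The overstatement is conditional on the 5.3.2 premise and limited to active-arm patients who are both off drug and unmeasured. With assumed rates of 30% and 9%, it runs from about 0.4 points (m=2%) to at most 2.1 points (m=10%), and post-withdrawal lipid sampling makes the lower part more likely.

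The documents do not support a reading in which the trial's efficacy conclusions are at risk: the endpoint lies outside the step-down procedure, so no alpha-controlled conclusion changes.

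**What to change.** Amend SAP 5.3.3 as follows.

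1. **Model.** Compare arms by logistic regression with treatment, randomisation stratum and baseline LDL-C. Report a standardised risk difference with its 95% CI, because an odds ratio alone does not give the percentage-point difference of interest.
2. **Weeks 12 and 24.** Derive response for every FAS patient by applying the 70 mg/dL threshold to the multiply imputed LDL-C data needed for the step-down, and combine by Rubin's rules. SAP 5.3.2 writes its on-drug and off-drug rules for Week 12 only, so the Week 24 rule should be written out. The step-down needs it in any case.
3. **Week 52.** Either apply the same imputation rules to both continuous LDL-C and response, or keep observed-case for both and add a sensitivity analysis with all randomised patients in the denominator. Imputing only one would create a new mismatch.
4. **Sensitivity.** Keep the observed-case chi-square or Fisher test.

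The cost is SAP wording, a little extra programming and probably a slightly smaller reported response difference. No new data are needed.
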